The research team will meet on a weekly basis to review study progress. The study team will also discuss any procedural difficulties, recruitment issues, randomization issues, and adverse events at this meeting (and before if needed). If there are consistent issues with the logistics, feasibility, or acceptability of the assessment visits or intervention calls (e.g., participant complaints about length of visits, frequent missed calls), we will review our methods and alter the study protocol as needed. For this pilot study, we will not plan to perform interim analyses. However, we will review feasibility/acceptability ratings of phone sessions in an ongoing manner, and if they are consistently low for a certain topic during the proof-of-concept

trial, we will review and alter that topic accordingly. This is in line with the purpose of this proof-of-concept trial, to trial and refine the newly developed intervention and study protocol.

D. Adverse event reporting guidelines

We will follow all PHRC guidelines with respect to reporting unanticipated problems, including adverse events. Specifically, when a serious or nonserious adverse event occurs, the PI will review the event to determine if it was possibly or definitely related to participation in the research. For all unanticipated problems and unexpected adverse events deemed related or possibly related to the research, we will complete and submit an “Other Event report through Insight/eIRB” as soon as possible and within 5 working days/7 calendar days (as defined in the May 2017 Reporting Unanticipated Problems Including Adverse Events report). At Continuing Review, we will provide a summary of all unanticipated problems as per PHRC protocol. Finally, if there are unanticipated problems, especially if serious or recurrent, the PI ([name]) will amend the protocol if it is deemed necessary to protect the safety and welfare of the participants.

X. REFERENCES

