If patients, as identified above, meet study criteria and remain interested in the study, the coordinator or other study staff will mail or send an electronic copy of the IRB-approved consent form for patient review, and will schedule an in-person visit at MGH. We will follow the MGB IRB guidelines around email contact, specifically that we will send all emails via an encrypted, SEND SECURE system, or that we will send them in a non-encrypted manner but only with the person's approval and understanding of the risks associated with non-encrypted email (i.e., that there could be loss of confidentiality). This will be discussed as part of the phone screen. This will allow patients to have adequate time to read the consent form. Informed consent will be obtained in person at MGH during the initial baseline visit by a trained study staff member (PI or research coordinator). Before collecting any data, the study coordinator will review the consent form during the study visit and will allow the patient to ask any questions he or she may have; the study PI will also be available to answer any questions. To ensure that participants have the capacity to provide informed consent, we will ask potential participants to describe their

understanding of the study's purpose and their role. They will also be asked for their permission to be contacted about participation in future studies. We will not exclude patients on the basis of race, ethnicity, or gender.

C. Treatment assignment/randomization

Proof-of-concept trial: For the initial trial, all participants will receive the PP-MI intervention and there will be no randomization.

V. STUDY PROCEDURES

A. Study visits and parameters to be measured

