Enrollment/Baseline Assessment (Visit #1): Patients who are interested in participating in the study and are eligible per the phone screen will come to the MGH TCRC for their initial study visit. At this time, informed consent will be obtained by a trained study staff member (PI or research coordinator). After providing informed consent, participants will provide demographic and medical information (e.g., medical comorbidities, weight history) and complete self-report measures to assist in characterization of the sample. Furthermore, height, weight, body mass index (BMI), waist circumference, body composition, and blood pressure will be obtained, and 5 mL of blood will be drawn for measurement of lipids, A1C, and CRP. We will also ask participants to report their weight at home the next day, for consistency. We also will perform a six-minute walk test⁷⁶ (6MWT) to assess functional exercise capacity. Finally, we will provide participants with an Actigraph GT3X+ accelerometer,⁷⁷ which they will be asked to wear for 7 days (minimum acceptable use is 4+ days with 10+ hours of recorded data). Participants will be given the option to complete Visit 2 remotely. If the participant chooses to complete the visit remotely, they will be given all the materials needed to mail the Actigraph back during their first visit.

Intervention Introduction (Visit #2; In person): This visit will take place approximately 1 week after Visit #1. Participants will return their accelerometer and study staff will check for sufficient wear time. If wear time is insufficient, the participant will be asked to wear it for another week and delay their Visit #2. If there is sufficient wear time participants will next be provided with a Fitbit Inspire 2 to track activity. They will set up the Fitbit with the research coordinator, using a study-provided login so that the study staff can access participants' Fitbit data during the study. After the study ends, participants will keep the Fitbit and will be instructed to change the account to a private one for ongoing personal use. They will then meet with the study interventionist for an introduction to the PP-MI intervention. Participants will be remunerated \$40 after this visit.

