10-Week Follow-Up (Visit #3): After completion of the intervention, participants will wear the accelerometer for 7 days (the device will be mailed to them so they can start wearing it the day after their final intervention call). They will then return to the TCRC for another in-person assessment where they will return the accelerometer and repeat all measures done at Visit #1. At this time participants will also complete an exit interview with a staff member who has not been in contact with them previously to provide feedback about their experience in the study. Participants will be remunerated \$60.

For participants who withdraw prior to completing the intervention: In the event that a participant withdraws from the study prior to completing all 10 weeks of the intervention, we will ask them to complete a different exit interview that is specifically for participants who decide not complete the study, in order to better understand their reasons for withdrawing. We will schedule these interviews as close as possible to the time that a participant withdraws. For those participants who have already withdrawn, we will send them an opt-out letter followed by a phone call after two weeks inviting them to complete the exit interview. All exit interviews will be scheduled with a staff member who has not been in contact with them previously. Participants will be remunerated \$50 for this phone call.

B. Drugs to be used

No drugs will be administered.

C. Devices to be used

No medical devices will be used.

D. Procedures/surgical interventions, etc.

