Feasibility and acceptability: We will ask participants receiving PP-MI to rate each topic on ease and usefulness on a scale from 0-10 (0=not at all easy/helpful, 10=very easy/helpful). We will also collect exit interview data from proof-of-concept trial participants to get more detail about what they liked or did not like about the study overall and any suggestions they have for improvement.

Self-report measures: These will be collected at baseline and 10 weeks.

- Optimism: Life Orientation Test – Revised (LOT-R)⁷⁹
- Depression and Anxiety: Hospital Anxiety and Depression Scale (HADS)⁸⁰
- Motivation (stage of change): University of Rhode Island Change Assessment (URICA)⁸¹
- Self-Efficacy (general and exercise-specific): General Self-Efficacy Scale⁸² and Self-Efficacy for Exercise Scale⁸³
- Internalized Weight Bias: Weight Bias Internalization Scale – Modified (WBIS-M)⁸⁴
- Exercise Identity: Exercise Identity Scale (EIS)⁸⁵
- MBS-specific Diet and Vitamin Adherence: Bariatric Surgery Self-Management Questionnaire⁸⁶
- Physical Activity and sedentary time (self-reported): International Physical Activity Questionnaire (IPAQ)⁶⁹
- Household Members Survey
- Social Support and Eating Habits Survey⁸⁷
- Social Support and Exercise Survey⁸⁷

Objectively-measured physical activity: These measures will be collected at baseline and 10 weeks using the Actigraph GT3X-BT.

- Moderate-to-vigorous physical activity in met-minutes/week and mean minutes/week
- Light physical activity in met-minutes/week and mean minutes/week
- Steps in mean number/day
- Sedentary time in mean minutes/day

Health-related measures: These will be assessed at baseline and 10 weeks.

- Weight, height, body composition, and waist circumference, assessed by trained MGH TCRC nurses during in person visits. Weight, height, and waist circumference will be measured and self-reported by the participant during remote visits.

- Blood pressure (in mm Hg), assessed via MGH TCRC nurses using their protocol during in person visits. Blood pressure will not be collected during remote visits.
- Lipids, A1C, and CRP via blood draw by MGH TCRC nurses during in person visits. Phlebotomists at Quest Diagnostics Service Center will complete the labwork for remote visits.
- Six-minute walk test, assessed by MCH TCRC nurses using their established protocol during in person visits. Six-minute walk test will not be completed during remote visits.

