All participants will be asked to complete all measures at all time points, if possible. However, should a participant decline a certain measure or choose not to attend a follow-up visit, we collect as much data as possible from that person and proceed with all collected data. While we will try to avoid it, we expect there will be missing data in this study.

VI. BIOSTATISTICAL ANALYSIS

A. Specific data variables being collected for the study

We will collect data from 12 participants in the proof-of-concept trial (assessments at baseline and 10 weeks plus weekly session ratings and exit interviews). Assessments will include the measures detailed above.

B. Study endpoints

Proof-of-concept trial: the primary goal of this phase is to refine the intervention to a place where it is feasible and acceptable. We will aim to obtain follow-up data from at least 10 participants. Feedback from this trial will inform any necessary further modification of the intervention or procedures prior to beginning the RCT.

C. Statistical methods

Proof-of-concept trial:

This small proof-of-concept trial is designed to test initial feasibility and acceptability of the newly developed intervention and to refine the intervention as needed.

Feasibility. Descriptive statistics will be used to calculate proportions to test feasibility, defined as % of sessions completed.

Acceptability will be measured with means and standard deviations of participants' ratings of session ease and utility on a 0-10 scale (0 = very difficult/not at all useful, 10 = very easy/very useful). Cutoffs will not be used to determine feasibility and acceptability for this study as the sample is so small, and the goal of Aim 2 is to refine the intervention content and procedures. Rather, completion rates and participant ease and utility ratings will be examined in combination with open-ended feedback to inform further refining.

Exploratory outcomes. For physical activity and all other psychological, behavioral, and health-related outcomes, we will model within-subjects pre-post changes in each outcome using a mixed effects regression model with a random intercept for each participant, to account for missing data. Given the sample size, tests of statistical significance will be exploratory. However, the effect size (Cohen's d) of the within-subjects change in each outcome measure from baseline to 10 weeks will be estimated to assess for a signal of intervention effect.

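### Sedentary time in raw minutes per day moves with accelerometer wear in a one-arm pre-post comparison; separately, the remote-visit rules need reconciling with an in-person Visit #3

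*Combined protocol and SAP*

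**What the plan says.** **Accelerometer.** Section V.E lists sedentary time as a daily mean in minutes, measured at baseline and 10 weeks, alongside light activity, moderate-to-vigorous activity and steps. V.A (Visit #1) asks for 7 days of wear and accepts a recording with at least 4 days and at least 10 hours. Under Visit #2, staff check the returned baseline recording and ask for another week if it falls short. Under Visit #3, the device is mailed out, worn for 7 days and handed back at the visit; no check or repeat week is described. VI.C models the pre-post change in each outcome with a random intercept per participant and reports Cohen's d. It mentions no adjustment for wear.

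**Visit mode.** IV.B states "Informed consent will be obtained in person at MGH during the initial baseline visit by a trained study staff member". The only remote option offered in V.A is for the second visit: "Participants will be given the option to complete Visit 2 remotely". No health measures are listed there. At 10 weeks participants "return to the TCRC for another in-person assessment where they will return the accelerometer and repeat all measures done at Visit #1". VII.A places blood draws at Visits #1 and #3, by a TCRC research nurse. Yet for the health measures V.E says "These will be assessed at baseline and 10 weeks" and then adds remote rules: "Weight, height, and waist circumference will be measured and self-reported by the participant during remote visits", and "Phlebotomists at Quest Diagnostics Service Center will complete the labwork for remote visits". Blood pressure and the walk test are not done remotely. Should a participant "choose not to attend a follow-up visit, we collect as much data as possible from that person and proceed with all collected data". V.A also collects a home weight after Visit #1: "We will also ask participants to report their weight at home the next day, for consistency".

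**The concern.** Sedentary minutes per day equal the sedentary share multiplied by the minutes worn. A participant whose behaviour does not change, but who wears the device longer or for less time at 10 weeks, shows a change in the outcome. A control group would normally absorb a general drift in wear; here there is none. The outcome bears on the intervention, since one of its weekly topics is reducing sedentary time. VI.C will read d as a signal of effect, and VI.D would consider enlarging the sample if changes do not go in the expected direction, so the sign of these changes can influence a decision.

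On visit mode, the remote rules cover measures taken only at baseline and 10 weeks. Baseline is in person, so the rules can apply only to Visit #3, which is itself written as in person. If some Visit #3 assessments were remote, a participant's own measurement could be set against a nurse's and enter the change score with nothing to mark it.

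**Working it through.** The plan states no power calculation, SD or effect size, so it offers no figure to reproduce. Values marked (A) are assumptions.

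**1. Sedentary time and wear**
- Formula: sedentary min/day = share × wear minutes.
- At a 60% share (A): 10 h gives 0.6 × 600 = 360 min; 14 h gives 0.6 × 840 = 504 min. Both recordings meet the minimum.
- Per hour of wear: 60 × 0.5 = 30 min to 60 × 0.8 = 48 min (shares 50-80%, A); 36 min at 60%.
- In d, for a one-hour change in mean wear at a 60% share: 36/60 = 0.60 or 36/90 = 0.40, with an SD of change of 60 or 90 min (A).
- For scale at n = 10 (the follow-up target in VI.B): SE of a paired d near zero = 1/√10 = 0.32; 95% half-width of the mean change = t(9)/√10 = 2.262/3.162 = 0.72 SD of change.
- As a share of wear, the same scenario gives 60% at both times, so the shift is 0.
- Limit of that remedy: take 13 h at 60% (468 of 780 min) and add one hour spent wholly sitting. Raw minutes rise by 60. The share becomes 528/840 = 62.9%, a rise of 2.9 points. The artefact shrinks but does not vanish.

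**2. Which measures a remote Visit #3 would affect**
- *Weight:* with a constant home-scale offset c, home follow-up minus clinic baseline = true change + c. Home minus home = (W1 + c) − (W0 + c) = true change. The baseline home weight exists, but the plan does not name which baseline weight enters the model.
- *BMI:* needs only the Visit #1 clinic height at both times.
- *Waist:* no home value is collected at baseline, so no same-mode pair can be formed.
- *Blood pressure, walk test, body composition:* no remote version, so these would be missing rather than mode-mixed.
- *Bloods:* V.E and VII.A differ on who draws them. Nothing shows a shift in the assay.

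**3. Size of a mode shift, if any**
- With m of 10 remote (A) and offset b (A), the mean change moves by (m/10) × b. Per 1 kg or 1 cm this is 0.2, 0.3 or 0.5 for m = 2, 3 or 5.
- With p = m/10 and k = b in SDs of change, spurious d = p·k/√(1 + p(1 − p)k²). For k from 0.25 to 1: m = 2 gives 0.05 to 0.19; m = 3 gives 0.07 to 0.27; m = 5 gives 0.12 to 0.45. The matching half-width is 0.72.
- VI.C does not define the denominator of d. On the baseline-SD scale, with equal SDs at both times and pre-post correlation r (A), bias and half-width are both scaled by √(2(1 − r)). At r = 0.8, m = 5, k = 1 the bias is 0.5 × √0.4 = 0.32, against a half-width of 0.715 × √0.4 = 0.45. Changing the scale makes the bias no smaller relative to precision.
- Direction is unknown. With 5 of 10 remote and an SD of change of 4 to 6 cm (A), a waist offset of −3 cm gives d of −0.35 to −0.24; an offset of +2 cm gives +0.24 to +0.16.

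**4. Precision if remote waist values are set aside**
- t(n−1)/√n: n = 10, 0.72; n = 8, 0.84; n = 7, 0.92; n = 5, 2.776/√5 = 1.24 SD of change.

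**The case against.** On sedentary time: V.E states a unit and does not forbid adjustment for wear; the instruction to repeat the Visit #1 measures might be taken to carry the wear minimum over to 10 weeks; light activity and steps also depend on wear, so sedentary time is not unique; and a share is not fully wear-proof. The last two stand, and they shape the fix. The first two do not close the gap: nothing commits the analyst to an adjustment, and nothing says what happens to a short follow-up recording.

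On visit mode: the sections can be read as a default with an exception. Visit #3 is in person, and the remote rules say what can still be gathered from someone who does not attend. The missing-data paragraph of V.E makes that plausible, but it does not say so, and VII.A still conflicts with V.E over who draws the blood.

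A reader might infer that remote weights would be compared with clinic baselines. The documents do not support that: a home weight is collected the day after Visit #1, expressly for consistency, so a like-for-like pair is available. Nor do they support inferring a laboratory shift in the bloods, or that remote Visit #3 assessments will in fact take place.

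Finally, all these outcomes are exploratory in a pilot of 10 to 12 people. That stands, and it limits the weight of the point.

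**Conclusion.** A minor point with a cheap remedy. The sedentary-time part stands on its own and does not depend on any remote visit: each hour of difference in mean wear moves the outcome by 30 to 48 min/day at an assumed 50-80% share. At a 60% share this is a d of 0.40 to 0.60 for an assumed SD of change of 60 to 90 min. That exceeds one standard error at n = 10 but lies inside the 95% half-width. Whether wear will change, and in which direction, cannot be known from the documents.

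The visit-mode part is mainly a matter of reconciling text. Any bias is small unless many follow-ups are remote, is avoidable for weight, and is nil if every Visit #3 is in person. Only waist lacks a same-mode baseline. Feasibility (session completion) and acceptability (session ratings) are untouched, so the point does not call the trial's main purpose into question.

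**What to change.** **Main change (V.A, V.E, VI.C)**
1. Analyse sedentary time as a share of wear time, or adjusted for wear time. Keep minutes per day as a descriptive figure.
2. Report mean wear hours at baseline and 10 weeks beside all accelerometer outcomes.
3. State that the 4-day, 10-hour minimum applies at 10 weeks as well as at baseline.

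**Secondary change (V.A, V.E, VII.A)**
1. Reconcile these sections on whether Visit #3 may be remote and who then draws blood.
2. If it may be remote, record the mode of each measure.
3. Pair a home-reported follow-up weight with the next-day home weight from baseline, and use the Visit #1 clinic height for BMI at both times.
4. Flag remote waist values and report the change in waist with and without them.
5. State that blood pressure, the walk test and body composition will be missing at a remote visit.

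**Cost.** Wording edits, one database field and slightly more analysis; no new measurement. A follow-up recording below the wear minimum would be lost to the accelerometer outcomes. The share still moves somewhat if added hours are mostly sitting. The waist report without remote values loses precision: the half-width rises from 0.72 to 0.84-0.92 SD of change with 2 or 3 set aside. With 5 set aside it reaches 1.24, so that report says least where a mode shift would matter most.

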PP-MI interventions to promote physical activity in other populations. Our group has tested PP-MI for health behavior change in randomized pilot trials patients after an acute coronary syndrome, in those with type 2 diabetes, and in patients with heart failure, with medium-to-large effect size changes in objectively measured physical activity in the PP-MI condition compared to the control.^{51,53,66,67}

PP pilot studies in post-MBS patients. To examine the relevance of PP-MI for post-MBS patients, we first conducted a survey study of members of online MBS support forums. In 95 respondents, positive affect and optimism were positively associated with adherence to MBS health behaviors and physical activity, supporting the idea that promoting positive psychological states could improve behavioral adherence and physical activity.³³

We also completed a qualitative study of 23 MGH Weight Center post-MBS patients that involved semi-structured individual interviews asking about participants' experiences with physical activity before and after surgery, their barriers and facilitators to activity, the types of emotions they experience in relation to physical activity, and their ideas and preferences about the planned intervention.⁶⁸ Interviews were transcribed and coded using inductive and deductive methods, and themes that emerged have informed the adaptation of PP-MI for this population.

C. Rationale/Potential Benefits/Overview of Proposed Research

Given: (a) the relationship between psychological well-being and health behavior adherence, (b) the preliminary efficacy of PP-MI interventions in other populations, and (c) the identified emotional barriers to adherence specific to the post-MBS population, this intervention, customized to apply to the unique experiences of post-MBS patients, has the potential to increase physical activity and reduce adverse events in a high-risk, high-yield population of patients. This would have direct benefits to patients and would impact public health, given that nonadherence to health behaviors is a major public health problem among patients with obesity.

II. SPECIFIC AIMS

We will conduct a one-arm proof-of-concept trial to refine the newly adapted intervention and study procedures.

Specific Aim 1: To pilot the adapted post-MBS PP-MI intervention with exit interviews for further refinement (N=10).

Hypothesis: We will recruit 10 participants and collect feedback from them that will aid in study refinement.

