D. Power analysis (e.g., sample size, evaluable subjects, etc.)

Proof-of-concept trial: We have not conducted a power analysis for this study because the primary aim is to establish and refine procedures, troubleshooting any unexpected problems. We anticipate a sample of N=10 to be sufficient to do this, although will consider expanding the sample if initial results do not show changes in outcome measures in the expected direction.

VII. RISKS AND DISCOMFORTS

A. Complications of surgical and non-surgical procedures, etc.

Blood sampling. We will collect blood at Visits #1 and #3. Risks of venous blood sampling include pain, bruising at the phlebotomy site, and emotional discomfort from the process. More rarely, participants may become lightheaded or experience syncope, or have an infection at the site. We will minimize these risks by ensuring that blood samples are drawn by study staff who have received specific training in phlebotomy (TCRC research protocol nurse) and have specific experience with this procedure. Procedurally, we will make sure participants are seated comfortably during and after the sampling, and we will temporarily (or permanently) halt blood draws if patients voice pain or discomfort. If participants experience problems after blood draws (e.g., concerns about infection), they will be able to reach a study physician at any time, who can help to assess the situation over the phone or arrange to have the participant seen by their own physician or by study physician staff to assess any problems.

B. Drug side effects and toxicities

No specific medications are being studied or administered solely for research purposes in this study.

C. Device complications/malfunctions

We will be utilizing two devices that measure physical activity in this study: the Actigraph GT3X-BT accelerometer and the Fitbit Inspire 2 activity tracker. These devices pose minimal risk. The accelerometer (ActiGraph GT3X-BT) used to measure activity is small, light, and without sharp edges. Immersing the device in water for a prolonged period may render it unusable but does not pose a shock risk. The Fitbit provided to participants for activity self-monitoring similarly poses minimal risk, given that it has no sharp edges, no potential to cause shocks, and no other known risks. We will educate participants about the use of both devices when providing the devices to them, and study staff will be available to troubleshoot any problems that arise during their use.

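### VI.C plans a Cohen's d of change for 10 to 12 participants with no small-sample correction (about 9% or 7.5% away from zero) and no named denominator

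*Combined protocol and SAP*

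**What the plan says.** VI.C (Statistical methods, Exploratory outcomes) models pre-post change in physical activity and in every other psychological, behavioral and health outcome "using a mixed effects regression model with a random intercept for each participant, to account for missing data". It then sets the role of testing: "Given the sample size, tests of statistical significance will be exploratory". Next comes the effect size, a Cohen's d, described thus: "of the within-subjects change in each outcome measure from baseline to 10 weeks will be estimated to assess for a signal of intervention effect". The section names no denominator for d, no small-sample correction and no confidence interval.

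On sample size, VI.A says "We will collect data from 12 participants in the proof-of-concept trial", VI.B says "We will aim to obtain follow-up data from at least 10 participants", and VI.D says "We anticipate a sample of N=10 to be sufficient to do this". There is no formal size calculation: "We have not conducted a power analysis for this study because the primary aim is to establish and refine procedures". The number of complete pairs per outcome is therefore about 10 to 12. It may be lower for some outcomes, since V.E expects missing data and does not collect blood pressure or the walk test at remote visits.

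**The concern.** VI.C plays down significance tests and turns to d for the reading of a signal, so d should be a defined quantity. Two things are open.

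- **Small-sample bias.** In a sample this small, the sample SD in the denominator makes d larger in absolute value, on average, than the quantity it estimates. A standard multiplier removes this, and the plan does not mention it.
- **Denominator.** A d of within-person change can be scaled by the baseline SD, an average of the two visit SDs, the SD of change, or the residual SD of the mixed model. These give different numbers from the same data. Several of them depend on how strongly the two visits correlate, which may well differ among outcomes as unlike as weight, CRP, accelerometer activity and questionnaire scores.

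At stake is how the exploratory table is read. The same shift in baseline-SD units could look modest for one outcome and large for another, and the scale could be chosen after the data are seen.

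**Working it through.** **Inputs.** Pairs: n = 10 (VI.D; VI.B minimum) and n = 12 (VI.A). The documents give no d, r or SD, so there is no planned figure to reproduce. The values of r and of the true d below are assumptions.

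**1. Small-sample bias.** For d scaled by the SD of change, with df = n − 1 and normal data, E[d] = δ / J(df), where J(df) = Γ(df/2) / [√(df/2) · Γ((df−1)/2)].

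- n = 10: J(9) = Γ(4.5) / (√4.5 · Γ(4)) = 0.914, and 1/J = 1.094, so inflation is 9.4%.
- n = 12: J(11) = Γ(5.5) / (√5.5 · Γ(5)) = 0.930, and 1/J = 1.075, so inflation is 7.5%.
- n = 8, as an illustration of missing pairs: J(7) = 0.888, so inflation is 12.6%.

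The same factors apply to the baseline SD, with df = number of baseline values − 1. For the average of the two visit SDs at n = 10, inflation runs from 4.4% (r = 0) to 8.9% (r = 0.95).

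**2. Bias against noise.** On the SD-of-change scale, Var(d) = [df/(df−2)] · (1/n) · (1 + nδ²) − δ²/J². For n = 10 and δ = 0.5 this is (9/7)(0.1)(3.5) − 0.25/0.914² = 0.450 − 0.299 = 0.151, so the SD is 0.39.

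| True d (n = 10) | Expected d | Bias | SD of d | Bias/SD |
|---|---|---|---|---|
| 0 | 0 | 0 | 0.36 | 0 |
| 0.2 | 0.219 | 0.019 | 0.36 | 0.05 |
| 0.5 | 0.547 | 0.047 | 0.39 | 0.12 |
| 0.8 | 0.875 | 0.075 | 0.43 | 0.18 |

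For an observed d of 0.5, the exact 95% CI is about −0.17 to 1.15 at n = 10 and −0.11 to 1.09 at n = 12.

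**3. Denominator.** With equal SDs σ at both visits, the SD of change is σ√(2(1−r)). Hence d by SD of change = d by baseline SD / √(2(1−r)).

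| Assumed r | Ratio | Baseline-SD d of 0.5 becomes |
|---|---|---|
| 0 | 0.71 | 0.35 |
| 0.3 | 0.85 | 0.42 |
| 0.5 | 1.00 | 0.50 |
| 0.8 | 1.58 | 0.79 |
| 0.9 | 2.24 | 1.12 |

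The residual SD of a random-intercept model in balanced data is σ√(1−r). At r = 0.9 that gives 0.5/√0.1 = 1.58. So one set of data at r = 0.9 could be reported as 0.5, 1.12 or 1.58, all consistent with VI.C.

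**4. Simulation check** (200,000 samples, n = 10, baseline-SD d = 0.5). Mean uncorrected d by SD of change was 0.463, 0.547, 0.864 and 1.224 at r = 0.3, 0.5, 0.8 and 0.9, which agrees with steps 1 and 3. Mean uncorrected d by baseline SD stayed at 0.547 to 0.549 throughout, and 0.914 × 0.547 = 0.50.

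**The case against.** The strongest reply is that little hangs on d here. Feasibility and acceptability come first, without cutoffs. No threshold is set for d, no later trial is sized from it, and the plan does not rank outcomes by it. The one decision linked to outcome changes, possible enlargement of the sample in VI.D, looks at their direction, and neither the correction nor the choice of SD can alter a sign. The bias is also a small part of the sampling error. All of this stands, and it makes the point minor.

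Two stronger readings are tempting and should be resisted.

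- A reader might infer that the d values will generally be too large. The documents do not support that. The small-sample bias is proportional to the effect and zero when there is none. Scaling by the SD of change gives a smaller d than the baseline SD whenever r is below 0.5. It also estimates a different quantity, which is not a bias. VI.C does not say that this scaling will be used.
- A reader might infer that d will sit on a different scale from the earlier trials that I.B describes "with medium-to-large effect size changes in objectively measured physical activity in the PP-MI condition compared to the control". Those are between-group results, but I.B does not say how they were standardized, so the scales cannot be compared from these documents.

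Nor is the baseline SD plainly the right denominator. Entry requires fewer than 200 minutes a week of self-reported activity (III.A), which may narrow the baseline spread of activity outcomes and so raise their d. The choice is a trade-off for the sponsor.

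What the reply does not answer is that the correction lowers both bias and variance at no cost, and that an effect size reported for every outcome needs a stated denominator.

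**Conclusion.** The point holds as a minor improvement to an exploratory analysis. Scaled by the baseline SD or the SD of change, uncorrected d is inflated in expectation by 9.4% at 10 and 7.5% at 12, away from zero and only where there is an effect. At a true d of 0.5 and n = 10 that is about 0.05, roughly one eighth of its sampling SD. These figures assume normal data and complete pairs.

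The denominator part is conditional. If the SD of change is used, d is 0.85 times the baseline-SD d at r = 0.3 and 2.24 times at r = 0.9, so values should not be compared across outcomes. This rests on assumed correlations and on equal SDs at the two visits. The documents show that the denominator is unspecified. They do not show that a misleading one will be used, and no decision in the plan rests on the size of d.

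**What to change.** Add one sentence to VI.C that does three things:

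- Name one standardizer in advance and use it for all outcomes.
- Multiply each d by the Hedges factor J for the actual degrees of freedom of that SD: 0.914 for 10 values, 0.930 for 12. With 12 at baseline and 10 at follow-up, the baseline SD has 11 df and the SD of change has 9.
- Report beside each d the raw mean change with its 95% CI and the SD of change, so that precision is visible and the SD-of-change version can be rebuilt.

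If the SD of change is chosen, add that d is not to be compared across outcomes.

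This needs no new data, visits or participants. The correction makes reported d about 7 to 9% smaller (1 − 0.930 = 7.0%; 1 − 0.914 = 8.6%). Any further change depends on the standardizer chosen and can go either way.
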